7.2. Screening and Critical Baseline Assessments

Information collected during the Screening Phase assessments described below represents key data that identifies and defines subject baseline status. This information is critical for the evaluation and comparison of subsequent safety and efficacy assessments.

Informed Consent: Informed consent will be obtained from the subject prior to the initiation of any study procedures or study-specific data collection.

Subjects who give written informed consent will enter a screening period of up to 35 days. A subject may be randomized when all screening procedures have been completed and eligibility criteria confirmed. During the screening period the following assessments will be performed:

Demographic parameters will be captured: year of birth, sex, race and ethnicity.

Medical/medication/family history will be assessed as related to the inclusion/exclusion criteria listed in Section 5. A complete medical history will be taken at the screening visit. Information from the medical history is important to establish the baseline condition of the subject, and will impact the safety monitoring assessments during the study. Any significant medical conditions affecting the subject in the past 5 years should be recorded on the Medical Conditions page of the eCRF. The history should include the following:

- Past or current conditions.
- Prior surgical procedures.
- Pharmacotherapy and chronic or recent use of any medication or herbal preparation.
- Prior immunosuppressive therapies, including type, number, and duration.
- Allergies and significant allergic reactions.
- Significant infections, or history of recurrent infection, including urinary and respiratory tract infections.
- Smoking history (current or previous smoker, number of cigarettes smoked per day).
- Cardiovascular medical history/risk factors (as detailed in the eCRF).

Urine Pregnancy Test: A test will be performed for women of child-bearing potential: monthly during the double blind treatment with investigational product (up to Week 52) and then at each clinic visit during the general and individualized follow up phases (see Time and Events Table in Section 7.1). Refer to the pregnancy section (Section 7.4.2).

Full physical examination: will include complete assessment of all organ systems including assessments of the head and neck (including eyes, ears, nose, throat, and thyroid gland), skin, musculoskeletal (including evaluation of both small and large joints), neurological, respiratory, and cardiovascular systems, gastrointestinal system and abdomen (including liver and spleen), lymph nodes and extremities.

Electrocardiogram: 12-lead ECGs will be obtained at screening. A single method (Bazett's or Fredericia's) must be used when calculating the corrected QT interval for determining subject eligibility, as described in the study reference manual (SRM).

American European Consensus Group (AECG) criteria: The 2002 American European Consensus Group criteria [Vitali, 2002] will be evaluated by the investigator to verify the subject's diagnosis of Primary Sjögren's Syndrome. The AECG criteria provide an assessment of six different parameters including: oral and ocular symptoms, oral and ocular signs, and objective measures of histopathology and biomarkers.

Unstimulated and stimulated salivary flow: Unstimulated and stimulated salivary flow rate will both be assessed as an entry criteria to ensure that subjects entered into the study have residual glandular function. Subjects with 0.0 mL/min unstimulated salivary flow rate may qualify for the study on the basis of stimulated salivary flow greater than 0.05 mL/min. Details of the collection procedure will be further specified in the SRM.

Oral dryness Numerical Response Scale (NRS): subjects are required to have symptomatic oral dryness as assessed by a score of at least 5 points on the 10 point NRS. The oral dryness NRS will be detailed in the SRM.

ESSDAI: subjects are required to have systemically active disease as determined by an ESSDAI score of at least 5 points. The ESSDAI [Seror, 2014] is an assessment of disease activity across twelve different clinically relevant domains for subjects with Sjögren's syndrome. ESSDAI will be assessed by the treating physician (preferably the same physician at each visit). Details and guidance regarding the application of the ESSDAI assessment will be provided in the SRM. A recent user's guide has also been published [Seror, 2015].

Serological Biomarkers: Quantification of serum analytes, autoantibodies [including anti-SS-A, SS-B], markers of B cells activation [may include but not limited to Beta-microglobulin, free kappa and lambda light chain], BLyS and other cytokines [may include but not limited to BLyS/Belimumab complex, IL-6, IL-21], chemokines [may include but not limited to CXCL13 and CCL19] and other analytes associated with immune activation or inflammation [may include but not limited to complement C3, C4, CH50, Cryoglobulin, CRP] or Sjögren's biology will be performed.

Urinalysis: will be performed as related to the eligibility criteria listed in Section 5.

Blood immunoglobulin (IgG, IgA, IgM) screening: will be performed as related to the eligibility criteria listed in Section 5.

Tuberculosis: Assessment of TB in the screening period is to be done via evaluation of the subject's history, physical examination of the subject and, if judged necessary by the Investigator, local laboratory testing. For subjects in Argentina only, the central lab will perform Quantiferon Gold testing.

Hematology and blood chemistry (clinical safety laboratory assessments): will be performed as related to the eligibility criteria listed in Section 5.

HIV, Hepatitis B and C screening: will be performed as related to the eligibility criteria listed in Section 5.

Salivary gland biopsy: The salivary gland biopsy surgical technique is described in the SRM. Training reference materials will be provided to site personnel who will perform this procedure.

Biopsy tissue will be shipped to a central histopathology laboratory for processing and assessment. The baseline biopsy can occur on Day 0 or at any time during the screening period provided the subject has met all other entry criteria prior. After the interim analysis, dependent on data, the biopsy may no longer be a mandatory requirement.

7.3. Efficacy

Planned time points for all efficacy assessments are listed in the Time and Events Table in Section 7.1. Time windows are provided for each study visit to allow flexibility in site and subject scheduling. All study visits should occur within the visit window of the scheduled study visit. Details regarding the execution of the efficacy assessments described below can be found in the SRM.

ESSDAI: The ESSDAI [Seror, 2014] is an assessment of disease activity across 12 different clinically relevant domains for subjects with Sjögren's syndrome. ESSDAI will be assessed by the treating physician (preferably the same physician at each visit). A recent user's guide has also been published [Seror, 2015].

Un-stimulated and stimulated salivary flow: Unstimulated salivary flow rate and stimulated salivary flow will be measured. Details of the collection procedure will be further specified in the SRM.

Salivary gland biopsy: The salivary gland biopsy surgical technique is described in the SRM. Training reference materials will be provided to site personnel who will perform this procedure.

Biopsy tissue will be shipped to a central histopathology laboratory for processing and assessment. After an interim analysis, dependent on data, the biopsy may no longer be a mandatory requirement.

Schirmer's test: is an assessment of lacrimal gland function in which a strip of filter paper is applied under the eyelid to measure the quantity of tear production. The technique for administration of this test will be described in the SRM.

PGA: the Physician's Global Assessment is a physician reported visual analogue scale that provides an overall measure of the subject's current disease activity. The assessment instrument and technique for administration will be described in the SRM.

Oral dryness NRS: A description of the anchors and directions for administering this scale will be provided in the SRM.

7.3.1. Patient-Reported Outcomes Assessments

Patient Reported Outcomes questionnaires should be completed by subjects before any other assessment at a clinic visit, in the order specified.

ESSPRI: the EULAR Sjögren's Syndrome Patient Reported Index [Seror, 2014] is an assessment of the severity of patients' symptoms in primary Sjögren's syndrome over the past 2 weeks, including dryness, pain (joint or muscular pains in arms or legs), and fatigue, on a 0-10 NRS for each symptom. The ESSPRI assessment tool will be detailed in the SRM..

Oral and Ocular Dryness: will be reported by subjects on a NRS from 0 to 10. The NRS will be translated into local languages. A description of the instrument anchors and technique for administering these scales will be described in the SRM.

PROFAD-SSI-SF: the Profile of Fatigue and Discomfort - Sicca Symptoms Inventory (Short Form) questionnaire is an assessment of fatigue, discomfort, and SICCA symptoms, on a 0-7 NRS for each item. Details will be provided in the SRM.

PtGA: the Patient Global Assessment is a patient reported numeric rating scale that provides an overall measure of disease severity. The assessment instrument and technique for administration will be described in the SRM.

Exit Interviews: Exit interviews will be conducted as shown in the Schedule of Events (Section 7.1) to explore subjects' experience with study treatment. Exit interviews are qualitative interviews conducted with study subjects to capture subject experiences in drug development on completion of participation in a clinical study. Interview questions designed to fully assess a subject's experience with a study medication are administered in a semi-structured format by a trained interviewer. Subject feedback will be captured in a data collection sheet as well as being audio-taped for subsequent transcription and qualitative analysis. The Exit interview technique and questions will be described in the SRM and training as well as training material references will be provided to site personnel who will administer the Exit interviews.

7.4. Safety

Planned time points for all safety assessments are listed in the Time and Events Table in Section 7.1. Additional time points for safety tests may be added during the course of the study based on newly available data to ensure appropriate safety monitoring.

7.4.1. Adverse Events (AE) and Serious Adverse Events (SAEs)

The definitions of an AE or SAE can be found in [Appendix 7](#).

The investigator and their designees are responsible for detecting, documenting and reporting events that meet the definition of an AE or SAE.

7.4.1.1. Time Period and Frequency for Collecting AE and SAE Information

- AEs and SAEs will be collected from the start of Study Treatment through the general follow-up period (see Section 4.3 and the Time and Events Table in Section 7.1)
- Medical occurrences that begin prior to the start of study treatment but after obtaining informed consent may be recorded on the Medical History/Current Medical Conditions section of the eCRF.
- Any SAEs assessed as related to study participation (e.g., protocol-mandated procedures, invasive tests, or change in existing therapy) or related to a GSK product will be recorded from the time a subject consents to participate in the study up to and including any follow-up contact.
- During the individualized safety follow-up phase (if applicable, see Section 4.3 and the Time and Events Table in Section 7.1), only SAEs assessed as related to the investigational product or to study participation, fatal SAEs, and designated AESIs (i.e., infections, malignancies, and depression/suicidality/self-injury) will be collected.
- All SAEs will be recorded and reported to GSK within 24 hours, as indicated in [Appendix 7](#).
- Investigators are not obligated to actively seek AEs or SAEs in former study subjects. However, if the investigator learns of any SAE, including a death, at any time after a subject has been discharged from the study, and he/she considers the event reasonably related to the study treatment or study participation, the investigator must promptly notify GSK.

NOTE: The method of recording, evaluating and assessing causality of AEs and SAEs plus procedures for completing and transmitting SAE reports to GSK are provided in [Appendix 7](#).

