3. OBJECTIVES AND ENDPOINTS

Objectives	Endpoints
Primary	

 Safety and tolerability of anti-BLyS / anti-CD 20 co-administration therapy and anti-BLyS and anti-CD 20 monotherapies 	
 Safety and tolerability; including incidence of SAEs and AESIs.
Secondary	

 Clinical efficacy of anti-BLyS / anti-CD 20 co-administration therapy and anti-BLyS and anti-CD 20 monotherapies Assessment of anti-BLyS / anti-CD 20 co-administration therapy and anti-BLyS and anti-CD 20 monotherapies on tissue B-cells. 	
 ESSDAI score over time Stimulated salivary flow over time Oral dryness numeric response scale over time B cell quantification within salivary gland biopsy at Week 24

Objectives	Endpoints
Exploratory 
 Assessment of mechanism and durability of effect of anti-BLyS/anti-CD 20 co-administration therapy and anti-BLyS and anti-CD20 monotherapies. 	
 Ocular dryness numeric response scale over time Lacrimal gland function as measured by Schirmer's test. Physician's Global Assessment (PGA) of disease activity over time Serologic markers over time Change in peripheral blood leukocytes including B cell subsets over time BLyS levels in blood Immunogenicity of rituximab and belimumab Pharmacokinetics of rituximab and belimumab Change from baseline in the cellular composition of the salivary gland Sustained efficacy of anti-BLyS/anti-CD 20 co-administration at Week 52 Additional exploratory biomarkers may be evaluated 
 Transcriptomic analysis of blood and salivary gland B and T cell receptor clonal analysis in peripheral blood and salivary gland Proteomic assessment of the saliva
Health Outcomes 
 Gather preliminary information on patient reported outcomes of anti-BLyS/anti-CD 20 co-administration therapy and anti-BLyS and anti-CD 20 monotherapies 	
 ESSPRI score (and individual scale subscores) over time Fatigue and Discomfort- SICCA Symptom Inventory (PROFAD SSI SF) over time Patient Global Assessment (PtGA) of disease activity over time Subject exit interviews

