Skin reactions	
Rituximab: Severe skin reactions such as Toxic Epidermal Necrolysis and Stevens-Johnson syndrome; some with fatal outcome, have been reported with rituximab.
	
Permanently discontinue treatment in the case of such an event with suspected relationship to treatment.

Posterior Reversible Encephalopathy Syndrome (PRES)	
Rituximab: Cases of PRES / reversible posterior leukoencephalopathy syndrome (RPLS) have been reported. Signs and symptoms included visual disturbance, headache, seizures and altered mental status, with or without associated hypertension. A diagnosis of PRES/RPLS
	
Medical monitor will be notified of any new neurologic symptoms (see Section 5.4.3). Medical monitor and investigator will consider the possibility of PRES in differential diagnosis.

Potential Risk of Clinical Significance	Summary of Data/Rationale for Risk	Mitigation Strategy
	requires confirmation by brain imaging. The reported cases had recognized risk factors for PRES/RPLS, including the patients' underlying disease, hypertension, immunosuppressive therapy and/or chemotherapy.	
Study Procedures		
Salivary gland Biopsy This procedure is associated with (a low) incidence of complications including bleeding and hematoma formation.	The reported incidence of bleeding and hematoma were 7.5% and 2.7%, respectively in a large case series [Santiago , 2012].	Subjects will be instructed to stop anticoagulant therapy (i.e., aspirin, NSAIDs, warfarin) prior to the procedure. Also, the biopsy will be performed by qualified physicians, surgeons or dentists and the personnel performing the biopsy will be required to undergo study-specific training in the performance of this procedure.

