11. First & second dose of belimumab will be administered in clinic by subject or caregiver. A patient alert card will be sent home with the subject each time belimumab is dispensed for home administration.
12. Week 24 biopsy may be taken on a separate day from the other required assessments within the Week 24 study visit window.
13. Week 52 biopsy is optional. Trancriptomics will only be performed if biopsy is taken.
14. If test otherwise performed within 3 months prior to first dose of study treatment, testing at screening is not required.
15. Informed consent for optional substudies e.g.,genetics must be obtained before collecting a sample.
16. If additional tests (e.g., pulmonary function tests, EMG, MRI) are required to complete ESSDAI assessment, these should be scheduled as close as possible to the stipulated study visit window.
17. From signing of consent until initiation of study treatment, only SAEs related to study participation will be collected.
18. From the end of general follow-up phase through the last contact (including the individualized safety follow-up phase), only designated AESIs (i.e., infections, malignancies, and depression/suicidality/self-injury), fatal SAEs, and SAEs assessed as related to the investigational product or to study participation will be collected.

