7.4.1.4. Adverse Events of Special Interest

A number of adverse events of special interest have been identified as part of the risk assessment outlined in Section 4.7.1 due to the co-administration of two biologics and will be monitored for the duration of the study. These AESIs include infections (including opportunistic), systemic infusion / injection reactions, hypersensitivity reactions, malignancy, psychiatric events (including suicidality), severe skin reactions (including Toxic Epidermal Necrolysis and Stevens-Johnson syndrome), immunogenicity, cardiac disorders, posterior reversible encephalopathy syndrome (PRES), PML, and AE's related to the biopsy procedure. The analyses of these events will be described in the Reporting and Analysis Plan.

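### Non-serious complications of the baseline biopsy that begin and are found before the first dose are not collected as AEs, so the biopsy AESI is under-counted

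*Protocol*

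**What the plan says.** Section 3 gives the primary endpoint as "Safety and tolerability; including incidence of SAEs and AESIs". Section 7.4.1.4 lists the AESIs. The list ends with "PML, and AE's related to the biopsy procedure", and the section says that the AESIs "will be monitored for the duration of the study". Section 7.4.1.3 requires non-serious AESIs to be followed up, so this category is not meant for serious events alone.

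The collection window is set in two places. Section 7.4.1.1 says "AEs and SAEs will be collected from the start of Study Treatment through the general follow-up period". Footnote 17 of the Time and Events Table (section 7.1) says "From signing of consent until initiation of study treatment, only SAEs related to study participation will be collected". For other occurrences between consent and dosing, section 7.4.1.1 permits, but does not require, an entry on the medical history page of the eCRF. Serious events related to study participation are recorded from consent, and protocol-mandated procedures and invasive tests are given there as examples.

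On timing, section 7.2 says "The baseline biopsy can occur on Day 0 or at any time during the screening period". Neither section 7.2 nor footnote 5 of the table states whether a Day 0 biopsy comes before or after the first injection. A second biopsy is scheduled at Week 24; a third at Week 52 is optional (footnote 13).

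The risk table in section 4.7.1 gives the expected complications: "The reported incidence of bleeding and hematoma were 7.5% and 2.7%, respectively in a large case series".

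**The concern.** Section 7.4.1.4 and the collection rule do not fit together for this AESI. One says that it is watched throughout the study. The other starts non-serious collection only at dosing, after most or all baseline biopsies have been done. Bleeding and hematoma, the two complications that the protocol names, are likely to be mostly non-serious. A site that follows section 7.4.1.1 and footnote 17 will put a minor hematoma after a screening biopsy on the medical history page, or nowhere.

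The AESI then has a different window for different biopsies: serious events only, in the period before dosing, for the baseline biopsy, and all events for Week 24 and Week 52. Its reported frequency will be too low as a measure of procedure risk. An analysis plan cannot repair this later, because events that were never recorded as AEs cannot be tabulated as such. The likely origin shows in Appendix 13: Amendment 4 added biopsy-related AEs to the AESI list and records no matching change to section 7.4.1.1.

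**Working it through.** This is mainly a check of which events the rules admit. The only precision figure that the protocol gives for the primary endpoint is the interval of 0.01 to 0.24 for 1 event in 20 (section 9.2.1). It reproduces: the 2.5% and 97.5% points of Beta(2,20) are 0.012 and 0.238. The point below does not depend on it.

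**Step 1: what is collected after a baseline biopsy**

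| Complication of the baseline biopsy | Collected as AE/SAE? | Source |
|---|---|---|
| Serious, any time from consent | Yes | 7.4.1.1, footnote 17 |
| Non-serious, starts after first dose | Yes | 7.4.1.1 |
| Non-serious, present before but first detected after first dose | Yes, under the AE definition | Appendix 7, 12.7.1 |
| Non-serious, starts and is detected before first dose | No; optional medical history entry | 7.4.1.1, footnote 17 |

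Only the last row is a gap.

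**Step 2: upper bound on its size**

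Inputs: bleeding 7.5% and hematoma 2.7% (section 4.7.1); about 70 subjects, maximum 120 (section 4.2); one baseline biopsy per subject. The protocol does not say how far the two complications overlap, so the range runs from full overlap (rate for either 0.075) to none (0.075 + 0.027 = 0.102).

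Expected number of subjects = N × rate:

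- N = 70: bleeding 70 × 0.075 = 5.25; hematoma 70 × 0.027 = 1.89; either, 5.25 to 5.25 + 1.89 = 7.14.
- N = 120: bleeding 120 × 0.075 = 9.0; hematoma 120 × 0.027 = 3.24; either, 9.0 to 9.0 + 3.24 = 12.24.

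The chance of at least one such complication among 70 is 1 − (1 − 0.075)^70 = 0.996 with full overlap, and 0.999 with none.

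These counts cover all complications of the baseline biopsy. They equal the uncounted events only if every one is non-serious and both starts and is found before dosing, so they are upper bounds.

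**Step 3: share of protocol biopsies affected**

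With Week 52 uptake u and no withdrawals, the baseline biopsy is 1/(2 + u) of all biopsies: 0.50 at u = 0, 0.40 at u = 0.5 and 0.33 at u = 1. The share is therefore one third to one half.

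**The case against.** The strongest reply is that the primary objective concerns the safety of the study drugs. Section 7.4.1.4 says that the AESIs were identified because two biologics are given together, and Appendix 7 ties an AE to use of a medicinal product. A hematoma before any study drug cannot be caused by it and, by randomization, should fall equally across arms. The biopsies that can inform on treatment, at Week 24 and Week 52, lie wholly inside the window. All of this stands, and it limits the consequence: the gap gives no reason to expect bias in the comparison of treatment safety between arms.

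It does not remove the conflict. This AESI is defined by a procedure, not by a drug. The biopsy is the only study procedure in the risk table, and baseline is one of its two scheduled non-optional occasions. Complications at baseline would also give a drug-free reference from about 70 subjects against which to read those at Week 24; the placebo arm has only about 10.

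Three stronger readings are tempting, and the protocol does not support them:

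- A reader might infer that complications of the baseline biopsy are never counted. Serious ones are collected from consent, and those that start or are first detected after dosing are AEs. For a Day 0 biopsy, later detection can be enough even if onset came before the injection.
- A reader might infer that a fixed half of biopsy complications is lost. The baseline biopsy is one third to one half of biopsies, and the loss is at most the non-serious, pre-dose part of its complications.
- A reader might infer that the decision after the interim on keeping the biopsy mandatory would lack its main evidence. Sections 7.2 and 7.3 say only that it depends on data; they do not say that it rests on procedural safety. Subjects counted toward the interim will also have reached Week 24, where biopsy events are collected in full.

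**Conclusion.** The point holds within these limits. Sections 7.4.1.1 and 7.4.1.4 and footnote 17 cannot all be followed for non-serious complications of the baseline biopsy that begin and are detected before dosing. As written, the biopsy AESI, and with it one part of the AESI incidence in the primary endpoint, is under-counted.

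The loss is at most about 5.3 to 7.1 subjects of 70, or 9.0 to 12.2 of 120. This assumes that the case-series rates apply to this population, that every subject has a baseline biopsy (the requirement may be lifted after the interim), and that all events are non-serious with onset and detection before dosing. The true loss will be smaller to the extent that events are serious, biopsies are done on Day 0, or events surface after the first dose; the protocol gives no figures for these. The effect is an understated procedure risk, not a distorted treatment comparison. It should be corrected because the data cannot be recovered afterwards and the correction is cheap.

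**What to change.** Reconcile the three places. In section 7.4.1.1 and footnote 17, add a sentence saying that AEs related to the biopsy procedure, serious or not, are collected from the baseline biopsy (or from consent), and refer to it in section 7.4.1.4. Report these events per biopsy as well as per subject, and keep them separate from treatment-emergent AEs so that pre-dose events do not enter the drug-safety tables. The sponsor could instead state in section 7.4.1.4 that this AESI covers on-treatment biopsies only. That would remove the contradiction but not recover the baseline information.

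The cost of the preferred change is one sentence in each of two places and opening the AE page of the eCRF before dosing for procedure-related events. The downside is a few more AE records and a slightly higher reported biopsy complication rate.
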